**IRB#: 08-155A(8)**

**1.0 PROTOCOL SUMMARY**

**1.1 Background**

There is a paucity of research on health-related quality of life (HRQL) in patients with gynecologic cancer in the 6-week period after major cancer surgery. Publications from other surgical disciplines have found that physicians tend to underestimate patient symptoms [1, 2]. The NIH, the FDA, and other regulatory agencies [3-5] have recognized patient-reported outcomes (PROs) as important in evaluating disease and treatment. Reducing the burden of treatment-related symptoms, especially during aggressive therapy, is an important cancer care goal. Gynecologic cancer surgery is associated with multiple moderate to severe symptoms and potential severe surgical complications, especially during the first postoperative month. Effective symptom control is depending on timely symptom assessment and sufficient feedback from patients to practitioners so that adjustment in symptom control can be initiated. Patients are often reluctant to report symptoms, enduring high levels of symptoms. The main purpose of this pilot study is to clarify whether patients are willing to self-report common toxicity information and quality of life using the WEBCORE system via the Internet. Web-based patient self-reporting from home between clinic visits could potentially improve the quality of post-operative care through earlier detection of symptoms; improve patient-doctor communication; and provide an efficient means for data capture in clinical trials evaluating the effects of surgical interventions on patient safety and HRQL [6]. However, it is not known as to whether patients will be able or willing to self-report symptoms during this period, or if clinicians will find this information to be clinically useful. If WEBCORE is utilized and patient feedback is generally positive, future investigation will be considered reasonable in order to assess the potential value of WEBCORE in postoperative care of cancer patients and in the setting of clinical treatment trials.

**1.2 Specific Aims**

**1.2.1 Primary Aim**

This pilot study will assess patient use of WEBCORE, an online system designed for cancer patients to self-record toxicity-related symptoms based on NCI Common Terminology Criteria for Adverse Events and global quality of life (QoL) by European Organization for Research and Treatment of Cancer (EORTC QLQ-C30). The primary aim is to determine whether electronic capture of patient-reported symptoms and QoL from home is feasible in women recovering from major gynecologic cancer surgery during the 6-week post-operative period.

**Memorial Sloan-Kettering Cancer Center  
IRB Protocol**

**IRB#: 08-155A(8)**

**1.2.2 Secondary Aims**

1. To measure the patient assessments of the usefulness of online symptom self-reporting in the early post-operative period, and clinician perceptions of its potential value in routine outpatient post-operative cancer care.
2. To evaluate the impact of online symptom self-reporting on patient care processes as measured by the number of telephone calls between nurses and patients, resulting interventions (as defined as new appointments scheduled, instructions to the patient to go to Urgent Care, or additions/subtractions/modifications to medications), and patient satisfaction with care delivery.
3. To identify most commonly reported and most distressing symptoms reported by patients after gynecologic cancer surgery and to measure quality of life (QoL) during the immediate postoperative period.

**1.3 Methods**

This is a single-arm pilot study in which patients with gynecologic malignancies will self-report their own symptoms and HRQL during the post-operative period using the online platform WEBCORE, which is currently in use in two other MSKCC protocols and has previously undergone extensive privacy and security review at MSKCC [7-13]. The purpose of the study is to clarify whether patients are willing to self-report common toxicity information, and QoL using the WEBCORE system via the internet.

In an evaluation of feasibility, 110 patients recovering from major gynecologic cancer surgery with home internet access and regular email use undergoing surgery for presumed or confirmed gynecologic cancer will be recruited from MSKCC outpatient clinics. Participants will be encouraged to logon to WEBCORE and complete a questionnaire once pre-operatively and then weekly starting 7 days after surgery until the 6-week post-operative period has ended. Entered information will be stored in a secure database located on a firewall-protected MSKCC server. Patients will be reminded to logon via email (Appendix 10). Patients who do not logon will receive a backup phone call to complete the symptom questionnaire, and to ascertain reasons for non-completion of the online survey.

A WEBCORE report summarizing patient symptom trends will be printed and made available to the clinician at the time of the post-operative visit. Additionally, if a patient submits a response that is concerning according to pre-specified limits set by the gynecologic oncology service, an automated email alert flagged as “urgent” and titled “severe Patient-reported symptom” will be sent in real-time to the research fellow, the designated RSA and the PI of the study. They will forward the email to the POA of the patient’s gynecologic oncologist and to the clinic nurse taking patient calls for that gynecologic oncologist that day. (This is the same system used presently to triage patient phone calls.) If the research fellow is not available, coverage will be provided by the designated RSA. In that event, the designated RSA

## Memorial Sloan-Kettering Cancer Center IRB Protocol

**IRB#: 08-155A(8)**

will notify the POA of the patient's gynecologic oncologist and the clinic nurse taking patient calls for that gynecologic oncologist that day. No specific responses to these emails will be required, but any actions taken in response to these alerts by clinicians will be tracked (ie, telephone calls, supportive medication prescriptions, new appointments made, etc) using a form emailed to the nurse after the automated email alert (Appendix 5) and the "Ambulatory Care Phone/Email Communication Form" in the EMR. The forms will be collected by the research fellow or by the designated RSA.

It will be emphasized to patients that there is no regular monitoring of information entered into WEBCORE, and that they should call their physician's office if they feel that they require medical attention. This will be emphasized to patients in the informed Consent, during a WEBCORE training session, and on the WEBCORE website. In addition, anytime a patient enters a potentially concerning response into WEBCORE, a popup box will appear on the screen reminding her to consider calling her physician.

If 80% of enrolled patients with home Internet access login to WEBCORE at least four times during the study period we will consider WEBCORE a strategy warranting larger scale evaluation. Patient assessment of the usefulness of WEBCORE will be measured via an exit survey. Clinician perceptions of the potential value of WEBCORE will be evaluated via an email survey and questions asked at a team meeting. Reasons for patient non-compliance will be assessed via results of the backup telephone calls to those who failed to login, and with the exit survey.

Potential benefits of this use of the WEBCORE platform in this context will be assessed by measuring the number and type of clinical interventions made in response to WEBCORE alerts, and by analyzing patient use of WEBCORE in relation to dates of surgery and development of documented post-surgical complications.

### **1.4 Significance**

Cancer patients commonly express an interest in shared decision-making and access to information towards treatment decisions [14-17]. Reducing the burden of treatment-related symptoms, especially during aggressive therapy, is an important cancer care goal. Gynecologic cancer surgery is associated with multiple moderate to severe symptoms and potentially severe adverse events and complications, especially during the first postoperative month. Effective symptom control is depending on timely symptom assessment and sufficient feedback from patients to practitioners so that adjustment in symptom control can be effective. Patients are often reluctant to report symptoms, enduring high levels of symptoms. If electronic patient self-reporting is found to be a feasible strategy for post-operative monitoring of symptoms, this could potentially become a widespread approach for communicating with patients between visits, automatically monitoring for concerning symptoms, reducing morbidity, and improving patient satisfaction overall. Real-time electronic reporting also affords an opportunity to increase the response time of physicians to

Memorial Sloan-Kettering Cancer Center  
IRB Protocol

IRB#: 08-155A(8)

severe toxicities, which may have particular relevance in the postoperative setting. Enhanced timely provider-patient communication about symptoms could reduce postoperative symptom burden, severity of complications and readmission/hospitalization. In the future, data collected online, could be analyzed and used for the development of patient education tools. In the clinical trial setting, this approach could improve the efficiency of collecting data from patients, and provide a source of symptom and HRQL information for use as clinical trial endpoints and/or toxicity documentation. This is consistent with the mission of the NIH [4], and will inform future grant submissions.

## 2.0 OBJECTIVES AND SCIENTIFIC AIMS

### 2.1 Objective

The overall objective of this study is to assess if online self-reporting of symptoms in the post-operative period is feasible and well-accepted by patients and clinicians.

### 2.2 Specific aims

#### 2.2.1 Primary Aim

To determine whether electronic capture of patient-reported symptoms from home is feasible in women recovering from major gynecologic cancer surgery during the 6-week post-operative period.

#### 2.2.2 Secondary Aims

- To measure patient assessments of the usefulness of online symptom self-reporting in the post-operative period, and clinician perceptions of its potential value in routine outpatient post-operative cancer care.
- To evaluate the impact of online symptom self-reporting **on patient care processes as measured by the number of telephone calls between nurses and patients, resulting interventions (as defined as new appointments scheduled, instructions to the patient to go to Urgent Care, or additions/subtractions/modifications to medications), and patient satisfaction with care delivery.**
- To identify most commonly reported and most distressing symptoms reported by patients after gynecologic cancer surgery and to measure quality of life (QoL) during the acute postoperative period.

**Memorial Sloan-Kettering Cancer Center  
IRB Protocol**

**IRB#: 08-155A(8)**

**3.0 BACKGROUND AND RATIONALE**

**3.1 Overview of Patient-Reported Outcomes (PROs)**

The purpose of this pilot study is to clarify whether patients are willing to self-report common toxicity information and quality of life using the WEBCORE system via the Internet. The impact on patients of cancer treatment and its adverse effects have been identified as essential outcomes for health professionals to consider during routine clinical practice and in clinical trials [3]. We are interested in two types of PRO's: HRQL and post-operative symptoms. HRQL has been described by Cella as, "the extent to which one's usual or expected physical, emotional and social well-being is affected by a medical condition and/or its treatment" [3]. Patients are interested in how surgery will affect their HRQL, and surgeons are interested in how to maximize their patients' HRQL. Clinically speaking, post-operative symptoms and HRQL are important indicators of the impact of surgery and could be used for earlier identification of complications. The FDA and NCI have asserted that these phenomena are best evaluated by patients directly without being filtered by clinicians or anyone else, in the form of patient reported outcomes (PROs)[5]

According to the 2006 FDA Draft Guidance on the use of PROs in clinical research, "a PRO is any report that comes directly from a patient about a health condition or its treatment without interpretation of the patient's response by a clinician or anyone else" [3,5]. As a result of this guidance, increasing emphasis has been placed on the appropriate use of PROs in clinical trials for detecting potentially concerning adverse effects and complications of cancer and its treatments. The NIH has sponsored a national initiative (PROMIS), a key project of the Roadmap Initiative, with an overarching goal to improve assessment methods of self-reported symptoms and HRQL outcomes in chronic diseases including cancer [4]. Included in that project is the development of a national databank of PRO items and instruments. The NCI and the American Cancer Society have both prioritized the integration of PROs into clinical practice and research, as demonstrated by the joint NCI-ACS-FDA hosting of the Patient Reported Outcomes in Cancer Trials (PROACT) conference in September of 2006. The conference sought to identify circumstances in which PROs are indicated, best practices for their use, and to establish a platform from which PROs can be efficiently incorporated into NCI clinical trails [18].

**3.2 Rationale for Patient Self-Reporting during the Post-Operative Period**

There is a paucity of data available regarding patient-reported symptoms and HRQL in gynecologic cancer patients in the immediate 6 weeks following surgery. In most trials of post-operative gynecologic cancer patients, HRQL surveys have been administered at baseline and 3 months post-operatively, time points that do not address the immediate post-operative period. The only well-publicized trial to do so was LAP-2, a Gynecologic Oncology Group (GOG) study comparing laparoscopy to laparotomy in early stage endometrial cancer that evaluated HRQL using validated

## Memorial Sloan-Kettering Cancer Center IRB Protocol

**IRB#: 08-155A(8)**

study have not yet been published. Due to the lack of data on symptoms and HRQL in post-operative gynecologic cancer patients, gynecologic surgeons' expectations of what symptoms "normally" occur in the post-operative period are based largely on anecdotal experiences. Furthermore, it is not clear which symptoms are most commonly reported and which are found to be most distressing for patients undergoing gynecologic cancer surgery.

While there is no data on PROs in patients recovering from major gynecologic cancer surgery, there is data comparing patient-reported symptoms to surgeon's observations from other surgical specialties. Studies in urology indicate that physicians tend to underestimate patient symptoms [1, 2]. For example, in a review of patient-reported complications after radical prostatectomy, authors noted a discrepancy in estimates of urinary wetness and post-surgical procedures compared to clinician reports [1]. Over 60% of study respondents reported some problem with wetness with 40% of patients stating that they drip urine when coughing or experiencing full bladders. These figures were also greater overall than the weighted average number of patients having "any incontinence" based on published literature. Published rates of erectile dysfunction after various radical prostatectomy techniques based on clinician reporting have been reported as inaccurately low as well compared to patient reporting. In a cohort study of self-reported sexual and urinary dysfunction among patients receiving nerve-sparing radical prostatectomy, patients did not report better-preserved postoperative sexual function despite younger age, better pre-operative sexual function and favorable clinical prognostic factors [19]. Recently, a group from M.D. Anderson presented their results of a randomized trial using a computerized telephone monitoring system to reduce postoperative symptoms in cancer patients after thoracic surgery [20]. Their goal was to see if enhancing timely provider-patient communication about symptoms would reduce post-operative symptom burden. They identified 5 most common and distressing symptoms reported by patients after surgery (pain, distress, sleep problems, shortness of breath and constipation). Providers were alerted via e-mail when symptom severity was exceeded. The used symptom tracking system was associated with fewer supra-threshold symptoms, reduced symptom severity, and lower symptom-related interference in cancer patients after thoracic surgery.

The discrepancy between surgeons' clinical impressions and patient's self-reported symptoms underscores the need for patient-reported HRQL data.

The lack of normative data available for the post-operative period has implications for patients and clinicians. Without information on the post-operative period from the perspective of the patient, it is difficult to adequately prepare patients for what to expect as they recover from major surgery. Montgomery et al. found, in a cohort of women undergoing ambulatory breast cancer surgery, that post-surgical pain and fatigue is related to pre-surgical expectations [21]. A Cochrane review of pre-

## Memorial Sloan-Kettering Cancer Center IRB Protocol

**IRB#: 08-155A(8)**

operative patient education in patients undergoing hip and knee surgery found a significant decrease in post-operative pain related to the intervention, but a decrease in pre-operative anxiety was observed [22, 23]. A qualitative study of nurses working on a surgical unit at a large teaching hospital in Ireland revealed a wide variation in skill and comfort delivering pre-operative education, which was related to knowledge of the material and lack of structured programs [24]. Pre-operative teaching is likely hampered by limited knowledge about what symptoms and effects on HRQL are to be expected during the post-operative period.

Home-reported symptom and HRQL data could be useful in the early identification of post-operative complications. At our service, between 2001 and 2005 there was an 8% rate of major complications (those that led to invasive radiologic intervention, re-operation, unplanned ICU admission, chronic disability or death within 30 days of surgery) associated with laparotomy on the gynecology service (internal data). When considering all complications, major and minor, the rate is close to 15%. Common complications include ileus, urinary tract infection, wound breakdown or wound infection. Less common but more serious complications include pulmonary embolism, bleeding, abscess and small or large bowel obstruction. While it is possible to identify characteristics that place patients at higher risk for complications, definitive predictors have not yet been established. Potentially a deviation from “normal” expected symptoms or HRQL in the post-operative course could be an early indicator of a developing complication (eg, increasing abdominal pain, intractable nausea, vomiting, appetite loss, change in bowel function, shortness of breath, excessive fatigue, etc). Effective symptom control is depending on timely symptom assessment and sufficient feedback from patients to practitioners so that adjustment in symptom control can be effective. Patients are often reluctant to report symptoms, enduring high levels of symptoms. Thus, enhanced timely provider-patient communication about symptoms could reduce post-operative symptom burden, severity of complications and readmission/ hospitalization. .

Web-based reporting could be an efficient form of data capture for clinical trials that evaluate the effects of surgical interventions on patient safety and quality of life. Online PROs minimize error and allow for prospective data banking. Web-based surveys have the potential to decrease the number of steps involved in data collection, maximizing efficiency and minimizing error. With home internet access becoming more widespread, online surveys may increase the accessibility to subjects and, in turn, increase response rate. Studies of response rates in patients and physicians have been conflicting so far—in some studies internet response rates are lower than those with pen-and-paper, though others show internet response rates at higher than 90% [25-27]. It is unclear if patients recovering from major gynecologic cancer surgery will be more or less apt to respond to questionnaires electronically, which is a rationale for conducting this study of feasibility.

## Memorial Sloan-Kettering Cancer Center IRB Protocol

**IRB#: 08-155A(8)**

The goal of post-operative care is to identify and deal with potential surgical complications, as well as promote a rapid recovery to the maximal level of functioning attainable, and to control symptoms. Patients are integral to these processes and are generally instructed to self-monitor for concerning symptoms and call or come to the Urgent Care Unit if specific or severe symptoms occur. It is therefore already recognized that the patient is best equipped to evaluate her own level of functioning.

However, there is currently no standard protocol for post-operative monitoring on the gynecology service at MSKCC, which is related to the lack of available data on symptoms in the post-operative period (Section 3.2). Patients who have a vertical skin incision closed with staples return on average will be discharged on postoperative day 6 (internal data). They return to the hospital between ten to fourteen days following surgery for staple removal and an incision check by a physician's assistant or fellow. A post-operative visit with the attending surgeon occurs anywhere between 3 and 6 weeks after surgery, depending on surgeon preference. If a patient has a problem after surgery, she will call the surgeon's nurse, or at night, the fellow on call. Patients who have more concerning symptoms such as dyspnea, intractable emesis, obstipation or bleeding will be encouraged to come to the Urgent Care Center or to the office. Less concerning symptoms like mild nausea, constipation or moderate pain often can be addressed via phone. This approach depends on the willingness of the patient to call and a clinician to respond and intervene in a timely manner. However, patients have different thresholds for calling. Patients could be enduring unnecessary discomfort and experience potentially life-threatening conditions due to under-reporting or underestimation of the severity of specific symptoms – but this is currently unknown due to lack of data in this area. Enhanced timely provider-patient communication about symptoms could reduce post-operative symptom burden, severity of complications and readmission/hospitalization.

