**IRB#: 08-155A(8)**

the post-operative period is feasible and well-accepted by patients and clinicians. This is a single-arm pilot study in which patients with gynecologic malignancies will self-report their own symptoms and HRQL during the post-operative period using the online platform WEBCORE.

Eighty patients with home internet access and regular email use undergoing laparotomy for presumed or confirmed gynecologic cancer will be recruited from MSKCC outpatient clinics. Enrollees will be sent weekly email reminders to login to WEBCORE from home (Appendix 10). Participants will be expected to complete the questionnaire once pre-operatively and then weekly starting 7 days after surgery until the 6-week post-operative period has ended. Entered information will be stored in a secure database located on a firewall-protected MSKCC server. If an enrolled patient fails to login and self-report within 24 hours of the automated reminder, a second reminder email will be sent. If the patient again fails to respond, a backup telephone call to the patient will be made by the clinical research fellow coordinating this study. The back-up phone call will be made within a week of the initial missed questionnaire. If the patient is unreachable, a total of 3 attempts will be made to reach the patient. The fellow will use a semi-scripted approach to complete the symptom questionnaire, and to ascertain reasons for non-completion of the online survey.

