## Memorial Sloan-Kettering Cancer Center IRB Protocol

**IRB#: 08-155A(8)**

### **4.2.3 Logging into WEBCORE**

Subjects are expected to login to WEBCORE once weekly from a home computer to fill out the online questionnaire. Subjects will be able to login to WEBCORE from any Internet-accessible computer whenever they wish to record symptoms, even if it is more frequently than the recommended weekly interval. Patients will be sent email reminders on the day they are due to login to WEBCORE which are identical to the email reminders currently in use in 04-020 (Appendix 10), and a follow-up email reminder email will be sent when they are overdue to login. Those who fail to respond to the follow-up email will receive a backup telephone call to administer the questionnaire and assess reasons for non-compliance.

Each time a patient logs in to the WEBCORE website, he or she will respond to items in the questionnaire, and these responses will be securely stored in the MSKCC Clinical Research Database (CRDB).

Technical assistance accessing the system will be available 24 hours. Patients will not be offered any financial incentives to login.

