**IRB#: 08-155A(8)**

**11.2 Primary Objective**

The primary objective of this study is to evaluate the feasibility of patients using WEBCORE to track their own symptoms and HRQL while recovering from laparotomy for presumed or confirmed gynecologic cancer. We will calculate summary statistics for several measures of utilization, including the frequency with which each user logs in and completes a WEBCORE online questionnaire; the proportion of patients who log in at each sequential week of follow-up; and when utilization occurs in relation to surgery and/or complications. If at the end of the study 58/79 are responders (a responder is a person who has logged in at least 4/7 times and completed at least half of the questions each time) then we will conclude that the use of WEBCORE in this population is feasible. If this hypothesis is true, we will consider the study results to suggest that WEBCORE is a strategy warranting larger scale evaluation [13]. Baseline patient characteristics and disease information will be examined via a logistic regression for their relationship to a patient's likelihood of being a responder. The following predictors will be considered: type of cancer, type of surgery, stage of disease, computer experience/age/education

In our analysis, we will look at WEBCORE utilization (1) over time and (2) in relation to the presence or absence of documented minor and major surgical complications. We will tabulate the proportion of users who logged in with or without a follow-up reminder email. We will assess for attrition of compliance over time by measuring the proportion of patients who login during each consecutive week of observation. Results of backup telephone calls made when patients have not logged in will be tabulated to assess if the reported symptoms of such patients differ from reports of patients who have logged in on time, and reasons for non-compliance. We will calculate the proportion of WEBCORE responders compared to the total number of enrollees (responders: enrollees), as well as the proportion of responders compared to total number of patients eligible (responders: eligible). Baseline characteristics for those who refuse enrollment will be compared to those who agree to participate.

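### Weekly login rates and the use-by-complication comparison can confuse hospital stay with not reporting from home, because the plan lists no discharge or readmission dates and defines no weekly windows

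*Combined protocol and SAP*

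**What the plan says.** Section 2.2.1 sets the primary aim as finding out whether "electronic capture of patient-reported symptoms from home is feasible in women recovering from major gynecologic cancer surgery". Section 4.1 has the questionnaire completed once before surgery and then "weekly starting 7 days after surgery until the 6-week post-operative period has ended". Section 3.3, describing the usual course, says that patients with a stapled vertical incision "on average will be discharged on postoperative day 6 (internal data". No SD, median or range is given, and no figure for other patients.

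On place of reporting, Section 4.2.3 says: "Subjects are expected to login to WEBCORE once weekly from a home computer to fill out the online questionnaire". The same section lets patients "login to WEBCORE from any Internet-accessible computer whenever they wish to record symptoms". Section 9.1 records the date and time of each access, but not where the patient was.

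Sections 9.1 and 11.2 plan two analyses that matter here. Attrition is assessed by "measuring the proportion of patients who login during each consecutive week of observation". Utilization is also examined "in relation to the presence or absence of documented minor and major surgical complications". Sections 1.3 and 4.1 list use in relation to complications among the ways of assessing potential benefit.

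Section 7.2 lists the data taken from the electronic record. Complication details are included; discharge date, length of stay and readmission are not. No section says how a report that falls due during a hospital stay is handled, or on which days week 1 begins and ends.

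**The concern.** The first due date falls one day after the only average discharge day in the document, so some patients are likely to be inpatients when the first report is due. Major complications are defined in Section 3.2 by events such as re-operation and unplanned ICU admission. It is reasonable to expect that these lengthen stay or cause readmission, although the documents do not say so.

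Two descriptive results are exposed. If week-1 use is low because patients are in hospital, the curve starts too low, and a true later fall to the same level would look like no attrition. If patients with complications spend more of the scheduled reports in hospital, they will show lower use even when they are equally willing to report from home. Section 11.3 already expects the sickest patients to use the system less, so a gap of that kind would look like confirmation. There is also an error in the other direction: a login made from a hospital bed cannot be told apart from a login at home.

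**Working it through.** The plan gives no figure for the share of patients in hospital on day 7, for week-1 use, or for use by complication, so there is nothing to reproduce. What follows is a range under stated assumptions.

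**Inputs from the protocol.** First report due on day 7 (4.1); mean discharge on day 6, stapled vertical incisions only (3.3); all complications about 15%, major 8% (3.2); 79 patients, responder defined by 4 of 7 logins, 80% considered acceptable (11.1).

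**Assumptions not in the protocol.** Length of stay is lognormal with mean 6 days and SD 1.5 to 4 days, and the day-6 mean is applied to all patients.

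**Step 1: share still in hospital.** With s² = ln(1 + (SD/6)²) and m = ln 6 − s²/2, P(stay > d) = 1 − Φ((ln d − m)/s). For SD 1.5: s = 0.246, m = 1.761, and for d = 7 the z value is 0.749, giving 0.227. For SD 4: s = 0.606, m = 1.608, z = 0.557, giving 0.289.

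| SD (days) | after day 7 | after day 8 | after day 14 |
|---|---|---|---|
| 1.5 | 22.7% | 9.8% | 0.0% |
| 2 | 26.2% | 14.7% | 0.3% |
| 3 | 28.7% | 19.9% | 2.1% |
| 4 | 28.9% | 21.8% | 4.5% |

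On 79 patients, 22.7% to 28.9% is 18 to 23; 4.5% is 3.6. A gamma shape with the same mean and SDs gives 24% to 32% after day 7 and also stays under 5% after day 14.

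**Step 2: effect on week-1 use.** Suppose true willingness is 80% in every week. If no inpatient logs in and only day 7 counts, observed use is 0.80 × (1 − 0.227) = 62% down to 0.80 × (1 − 0.289) = 57%. If half of the willing inpatients log in, it is 0.80 × (1 − 0.227/2) = 71% down to 0.80 × (1 − 0.289/2) = 68%, with hospital logins inside the figure. If week 1 stays open to day 14, the lowest value is 0.80 × (1 − 0.045) = 76%. The choice of window therefore matters more than the choice of SD.

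**Step 3: use by complication.** The group is small: 0.15 × 79 = 11.9, of which major 0.08 × 79 = 6.3. As an illustration only, take equal willingness of 80%, no inpatient logins, and 50% against 20% in hospital on day 7. Use is 0.80 × 0.50 = 40% against 0.80 × 0.80 = 64%, a 24-point gap from hospital stay alone. The 50% and 20% are assumed.

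**Step 4: outer bound for the responder count.** Suppose 20% to 30% of patients lose the first report entirely. If logins are independent, a responder rate of 80% on 4 of 7 corresponds to 64.7% on 4 of 6. The overall rate becomes 0.8 × 0.80 + 0.2 × 0.647 = 77%, or 0.7 × 0.80 + 0.3 × 0.647 = 75%. With logins clustered within patients (beta-binomial) it becomes 78% to 79%.

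**The case against.** Much can be said for the plan. Day 6 is a mean for one incision group, in a garbled sentence, and it falls before the due date. Attrition is measured per week, not on a single day. A second email follows after 24 hours and the backup call may come up to a week later, so a patient discharged on day 8 or 9 can still report from home. The calls ask why the report was missed, the reasons are tabulated, and the exit survey asks why the system was not used. These are descriptive results in a single-arm pilot.

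Most of this stands, and it limits the size of the problem. It does not remove it. The calls cover only missed reports, can fail after three attempts, and say nothing about logins made in hospital. Tabulated reasons do not change the weekly proportions. No week-1 window is written down, so the milder reading is not secured by the text.

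Four stronger readings are tempting and are not supported:

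- That 18 to 23 of 79 patients are affected. That figure is a day-7 cut-off under an assumed distribution.
- That complications are known to keep patients in hospital. Section 3.2 gives neither timing nor length of stay, and some complications may arise after discharge.
- That the plan counts inpatient logins as home use, or every patient in every weekly denominator. It states neither rule; it is silent.
- That the primary conclusion is undermined. The responder rule is defined by logins and completion wherever they occur, includes the pre-operative login, and allows three missed reports. The shift in Step 4 needs a first report that is lost outright, with no inpatient login and no later catch-up.

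**Conclusion.** The point holds as a limited one. Followed exactly, the plan cannot separate hospital stay from non-use at home in the weekly login curve or in the comparison by complication, and it cannot separate hospital logins from home logins. The direction of the net error is not fixed: missed inpatient reports lower apparent home use, and inpatient logins raise it.

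The size is unknown. It rests on a single subgroup mean, an assumed shape and SD, and an undefined window. Under those assumptions it runs from about a quarter of patients, if only day 7 counts, to under 5% if week 1 stays open to day 14. The complication comparison is the more fragile of the two, with only about 12 patients expected in the smaller group. Both results are descriptive and neither enters the 58/79 decision. The change is worth making because it is cheap and bears directly on the words about home in the primary aim.

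**What to change.** In Section 7.2, add the index discharge date and any readmission and re-discharge dates to the chart review already planned.

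In Sections 9.1 and 11.2:

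- Define the first and last day of each weekly window.
- Mark every scheduled report as at home or in hospital by one rule that treats completed and missed reports alike, for example the patient's location on the due date.
- Show weekly login proportions and use by complication for at-home reports beside the all-patient figures, with denominators.

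Leave the 58/79 responder rule as it is. If a sensitivity responder count is wanted, keep the pre-operative login and exclude only post-operative reports made in hospital, using the login date that is already recorded. Counting only reports made after discharge would drop the pre-operative login and lower the rate by construction. Because even the narrower exclusion can only reduce the count, present it as descriptive and do not test it against 58/79.

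The cost is a few date fields per patient and extra columns in tables already planned. Patient contact, schedule and sample size do not change.
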